9.4 Women of Childbearing Potential & Pregnancy

A female is considered of childbearing potential if she has reached 9 years of age or unless she is post-menopausal (no menses for 12 consecutive months), surgically sterilized (documented hysterectomy, documented bilateral salpingectomy, documented bilateral oophorectomy). Tubal ligation does not meet the definition of surgically sterile.

WOCBP must use an effective method of birth control during the study. The following are considered acceptable methods of birth control for this study: hormonal contraceptives (combined estrogen and progestogen or progestogen only, including oral, injectable, transdermal or injectable formulations); intrauterine device (IUD); intrauterine hormone releasing system (IUS); bilateral tubal occlusion or ligation if performed ≥ 3 months prior to Baseline; same sex partner or partner who has had a vasectomy; sexual abstinence .with a documented acceptable method of birth control if the subject becomes sexually active; female or male condoms with or without spermicide; or a cervical cap, diaphragm, or sponge with spermicide. Women with tubal occlusion or ligations or whose partner has had a vasectomy will be required to complete UPTs at the required timepoints if the procedure was done < 3 months prior to Baseline.

Before enrolling any subject in this clinical trial, the investigator must review guidelines about study participation including the topics below:

- Informed consent document
- Pregnancy prevention information
- Risks to unborn child(ren)
- Any drug interactions with hormonal contraceptives
- Contraceptives in current use
- Guidelines for the follow-up of a reported pregnancy

Prior to study enrollment, all subjects must be advised of the importance of avoiding pregnancy during participation in this clinical study and the potential risk factors for an unintentional pregnancy. The subject must sign an informed consent document stating that the above-mentioned risk factors and the consequences were discussed.

During the study, females who have reached the age of menarche should be instructed to contact the investigator immediately if they suspect they might be pregnant (e.g., missed or late

menstrual cycle). Study drug shall be held immediately if a subject is suspected to be pregnant and study drug must be permanently discontinued if pregnancy is confirmed. The investigator must immediately notify the medical monitor/CRO of any female subject who becomes pregnant any time during study participation, record the information on the pregnancy notification form and email the form to the CRO. Subjects found to be pregnant prior to Week 12 will be discontinued from study drug treatment, continue with study visits through Week 24 and follow up with pregnancy outcome. The site should follow-up with the subject periodically during the pregnancy for ongoing health and safety information through the end of the pregnancy, as applicable. The investigator is responsible for following the pregnancy through the end of the pregnancy and for providing the assessment of the healthy live birth or for reporting any abnormal outcome such as stillbirth, miscarriage, or deformity to the CRO/sponsor (Note: Congenital anomalies are considered SAEs and require separate reporting per Section 9.2.3).

9.5 Overdose or Misuse

There is no specific antidote for SB206. In the event of an overdose, best supportive care should be utilized. Methylene blue may be used to treat subjects exhibiting methemoglobinemia. The medical monitor/CRO/sponsor must be notified of any subject exhibiting signs of methemoglobinemia.

10 ANALYSIS

10.1 Hypothesis

This study is intended to formally evaluate the efficacy of SB206 10.3% QD against Vehicle.

The primary efficacy comparison will test the following hypotheses:

H0: The proportion of subjects with complete clearance is equal between SB206 10.3% QD and Vehicle;

H1: The proportion of subjects with complete clearance is different between SB206 10.3% QD and Vehicle.

10.2 Population

10.2.1 Sample Size Rationale

Approximately 850 subjects, 6 months of age and older, with a minimum of 3 and a maximum of 70 MC lesions at Baseline will be randomized in a 1:1 (active:vehicle) scheme. The sample size assumptions for this study were informed by the integration of the completed phase 3 studies [NI-MC301](#) and [NI-MC302](#). Multiple replications of simulated random sampling of the integrated NI-MC301 and NI-MC302 data was performed to ensure the sample size assumptions align with the proposed design of NI-MC304. This includes the 1:1 ratio (active:vehicle) and the percentages observed in NI-MC301 and NI-MC302 for each stratum of each of the stratification

factors: investigator type, number of randomized subjects per household, and baseline BOTE score that are planned for NI-MC304.

The analysis of the proportion of subjects with complete response of all treatable MC at Week 12 within the Intent-to-Treat (ITT) Population of the multiple replications of simulated random sampled integrated data yields rates of 20% for vehicle and 29.5% for SB206 10.3% QD with the covariate-adjusted treatment difference was 9.5%. A sample size of 850 subjects (425 subjects in the SB206 10.3% QD group and 425 subjects in the vehicle group) will provide 90% power for a 2-sided alpha test of size 0.05 to detect an absolute difference of 9.5% when the vehicle response rate is 20%.

10.2.2 Analysis Subsets

The Intent-to-Treat (ITT) analysis population will include all randomized subjects who have a signed informed consent or assent as applicable. The ITT analysis population will be used as the main analysis population for efficacy (primary and secondary) and exploratory endpoints. Subjects will be analyzed according to the treatment group to which they were randomized.

The Per Protocol (PP) analysis population will include all ITT subjects with no significant protocol deviations potentially having an impact on the efficacy evaluations. Subjects will be analyzed according to the treatment group to which they were randomized. The PP analysis population will be used as a supportive analysis population for the primary and secondary efficacy endpoints.

The Safety analysis population will include all ITT subjects who received at least one dose of the study treatment. Subjects will be analyzed according to the study treatment actually received. The Safety analysis set will be used for the summary of demographic and other baseline characteristics, prior and concomitant medications, exposure and compliance with the study drug, and all safety endpoints.

10.2.3 General Considerations

Continuous variables will be summarized by treatment group and visit, when applicable, using the number of subjects with non-missing data (n), mean, standard deviation (SD), median, minimum, and maximum. Categorical variables will be summarized by treatment group and visit, when applicable, using frequencies and percentages.

All statistical tests will be two-sided and will be performed with a significance level of 0.05, unless otherwise specified.

Additional details regarding the analysis of primary, secondary, exploratory, safety endpoints and all sensitivity analysis will be included in the SAP. The SAP will be finalized before unblinding and database lock.

10.3 Testing Procedures

10.3.1 Analysis of the Primary Efficacy Endpoint

The primary efficacy endpoint for this study is the proportion of subjects achieving complete clearance of all treatable molluscum lesions at Week 12 for the ITT population. Complete clearance of all MC at Week 12 is defined as having a lesion count of 0 at Week 12. The number and percentage of subjects with complete clearance at Week 12 will be summarized by treatment group.

The primary efficacy endpoint will be analyzed using a generalized estimating equation (GEE) for logistic regression with an exchangeable working correlation structure. The model will include treatment, investigator type (dermatologist vs other), Baseline BOTE score (no inflammation (BOTE = 0) vs. mild/moderate/severe inflammation (BOTE \geq 1) and number of randomized subjects per household (1 subject per household vs. 2 subjects per household), age and Baseline lesion count as factors. The odds ratio between SB206 10.3% and vehicle gel, 95% CIs for the odds ratio, and P-value for the covariate-adjusted treatment comparison will be presented; together with predicted proportions along with their associated 95% confidence interval. Only subjects who achieve complete clearance at Week 12 will be counted as responders for the primary analysis. Subjects who discontinue the study before the Week 12 analysis visit for any reason will be considered not to have achieved complete clearance at Week 12, even if the subject discontinues after a lesion count of 0.

As a sensitivity analysis, the primary efficacy analysis will also be applied to the PP population. Additional sensitivity analyses may be performed including analyses that utilize alternative assumptions from those of this primary method to ensure that efficacy results are not driven by the method of handling missing data.

10.3.2 Analysis of Secondary Efficacy Endpoints

The familywise error rate with respect to the primary endpoint and secondary endpoints will be strongly controlled at the $\alpha=0.05$ level using a hierarchical fixed sequence method testing strategy. If the primary endpoint is not statistically significant at the $\alpha=0.05$ level, the secondary efficacy endpoints will be considered not significant. If the primary endpoint is statistically significant at the $\alpha=0.05$ level, the secondary efficacy endpoints will be tested in the following hierarchical fixed sequence:

- Proportion of subjects achieving a lesion count of 0 or 1 of all treatable MC at Week 12
- Proportion of subjects achieving at least a 90% reduction from Baseline in the number of all treatable MC at Week 12
- Proportion of subjects with complete clearance of all treatable MC at Week 8
- Percent change from Baseline in the number of all treatable MC at Week 4

At each subsequent test of the secondary efficacy endpoints, if the secondary endpoint is not statistically significant at the $\alpha=0.05$ level, the remaining secondary efficacy endpoints will

be considered not significant. If the secondary endpoint is statistically significant at the $\alpha=0.05$ level, the next subsequent secondary efficacy endpoint will be tested following the sequence.

10.3.3 Population Analysis

10.3.3.1 Disposition

Subject disposition information will be summarized for all subjects by treatment group. Summaries will include: the number of subjects screened, the number of subjects in each analysis population, the number of subjects where study treatment stopped, primary reason for study treatment stopped, the number of subjects completing 12 weeks of the study, the number of subjects completed the study, and the primary reason for discontinuation.

10.3.3.2 Demographics and Baseline Characteristics

Demographic variables include age, sex, ethnicity, and race. Age will be calculated in years relative to the informed consent date.

Other baseline characteristics include lesion counts at baseline, baseline BOTE score, site type (dermatologist vs other), and age at and time since onset of symptoms of current molluscum episode. Demographic and baseline characteristics will be summarized for the Safety, ITT, and PP Populations.

10.3.4 Safety Analysis

No missing safety data will be imputed, and no inferential statistics will be done for any safety endpoints. Change from Baseline in abbreviated physical examinations and a summary of concomitant medications will be presented.

10.3.4.1 Adverse Events

All AEs will be coded using the Medical Dictionary for Regulatory Activities (MedDRA Version 23.0 or later).

A treatment-emergent AE (TEAE) is defined as those AEs that occurred any time on or after the first in-clinical application of study drug through the last application of study drug and those existing AEs that worsened during this same period. If it cannot be determined whether the AE is treatment emergent due to a partial onset date, then it will be counted as such.

TEAEs will be summarized by System Organ Class (SOC) and Preferred Term (PT). For the summary by SOC and PT, each subject will be counted only once within a SOC or a PT. AEs with an outcome of death, SAEs, TEAEs leading to discontinuation from study treatment, and TEAEs leading to discontinuation from the study will be summarized similarly.

TEAEs will be further summarized by worst severity and highest relationship with study treatment, separately. For the summary by worst severity, each subject will be counted only once

within a SOC or PT according to the worst reported severity. Similarly, for the summary by highest relationship with study treatment, each subject will be counted only once within a SOC or PT according to the highest reported relationship with study treatment.

Separate listings will be provided for the AEs with an outcome of death, SAEs, TEAEs leading to discontinuation from study treatment, and TEAEs leading to discontinuation from study.

The proportion of subjects with scarring and the proportion of subjects with keloid or hypertrophic scarring will be summarized descriptively.

10.3.4.2 Local Skin Reactions

The LSR composite score will be calculated by summing up all the numerical responses (0-4) to each individual parameter for a composite score that ranges between 0 and 24. The change from Baseline of the LSR composite score will be summarized descriptively. A table summarizing each LSR parameter (erythema, flaking/scaling, crusting, swelling, vesiculation/pustulation, and erosion/ulceration) score at each scheduled postbaseline assessment will be presented.

Additionally, a shift table comparing the baseline score for each LSR parameter to each scheduled postbaseline assessment will be presented for the Safety Population.

10.3.5 Other Analyses

A shift table comparing the baseline BOTE score to each scheduled post-baseline assessment will be presented for the Safety Population. Additional BOTE vs lesion count/complete clearance analyses may be explored and further detailed in the SAP.

10.3.6 Exploratory Analysis

The exploratory endpoints based on the proportion of subjects achieving complete clearance (at Weeks 2, 4) or 75% (at Weeks 2, 4, 8, 12), 90% (at Weeks 2, 4, 8) reductions will be analyzed in the same manner as the primary endpoint.

Likewise, the proportion of subjects achieving a lesion count of 0 or 1 of all treatable MC at Weeks 2, 4 and 8 will be analyzed in the same manner as the primary endpoint.

The change and percent change from Baseline in the number of treatable MC will be analyzed using a repeated measures mixed model for the respective visits with the same covariates as the primary model together with visits and treatment by visit.

Time to first complete clearance of all MC will be analyzed using Kaplan-Meier methods. The number and percentage of subjects achieving complete clearance, number and percentage of censored subjects, and Kaplan-Meier estimates of first quartile, median, and third quartile will be summarized by treatment group.

The proportion of subjects who have a recurrence of MC after the first visit at which complete clearance was observed will be summarized.

The subject-reported spread of MC to household members not in the study will be summarized descriptively including a breakdown of whether or not there was any spread and then a breakdown of the amount of spread within the household at each visit at the household level.

Investigator global severity assessment and investigator global impression of change will be summarized descriptively. Subject global severity assessment and subject global impression of change will be summarized descriptively.

Listings will be provided for the results from the study exit interview.

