$$X_{H_{i11}} = \begin{cases} 1, & \text{if subject has a baseline age 7 to } <8 \\ 0, & \text{otherwise} \end{cases}$$

$$X_{H_{i12}} = \begin{cases} 1, & \text{if subject has a baseline age 8 to } <9 \\ 0, & \text{otherwise} \end{cases}$$

$$X_{H_{i13}} = \begin{cases} 1, & \text{if subject has a baseline age 9 to } <12 \\ 0, & \text{otherwise} \end{cases}$$

$X_{H_{i5}}$  is the subject's baseline lesion count; treatment will be included in the class statement with PARAM=REF and REF=Vehicle. The working correlation will have an exchangeable structure. In the event of issues with convergence, an independent structure will be utilized. The model will include a repeated statement for subject household with household ID in the class statement. Also, the data structure will be ordered according to household ID and subject ID in household.

Treatment groups will be compared using a generalized estimating equation for logistic regression with an exchangeable working correlation structure. The model will include treatment, investigator type (dermatologist vs other), household number of randomly assigned subjects (1 subject per household vs 2 subjects per household), BOTE score at Baseline (no inflammation [BOTE=0] vs mild/moderate/severe/very severe inflammation [BOTE≥1]), age (0 to <3, 3 to <4, 4 to <5, 5 to <6, 6 to <7, 8 to <9, 9 to <12, and ≥12 years old), and baseline lesion count as factors. For subjects from a household with 2 subjects, the actual values of BOTE score at Baseline and investigator type will be utilized with the recognition that such subjects did not have further stratification according to investigator type and BOTE score at Baseline. The odds ratio between SB206 10.3% and vehicle gel, 95% confidence intervals for the odds ratio, and *P*-value for the covariate-adjusted treatment comparison will be presented together with predicted proportions along with their associated 95% confidence interval. The difference in proportion confidence interval will be calculated using the following formula:

$$(p_{SB206} - p_{Vehicle}) \pm z_{0.025} * SE$$

Where the SE =

$$\sqrt{\frac{p_{SB206}^2(1 - p_{SB206})^2 s_{SB206}^2 + p_{Vehicle}^2(1 - p_{Vehicle})^2 s_{Vehicle}^2 - 2p_{SB206}(1 - p_{SB206})p_{Vehicle}}{(1 - p_{Vehicle}) * \left( \frac{s_{SB206}^2 + s_{Vehicle}^2 - s_{Odds Ratio}^2}{2} \right)}}$$

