## 11.2 Secondary Efficacy Analyses

The secondary endpoints of the proportion of subjects achieving a lesion count of 0 or 1 of all treatable MC at Week 12, proportion of subjects achieving at least a 90% reduction from Baseline in the number of all treatable MC at Week 12, and the proportion of subjects with complete clearance of all treatable MC at Week 8 will be analyzed in the same manner as the primary endpoint.

Since the within-household correlation is expected to be small, the percent change from Baseline in the number of all treatable MC at Week 4 will be analyzed using a repeated measures mixed model for the respective visits with the same covariates as the primary model together with visits and treatment by visit interaction; an unstructured covariance matrix will be utilized. If the calculation of the percent change from baseline is influenced by outliers with calculated values >100%, then the influence of outliers will be avoided for analysis by censoring them so that all values were in the range of -100% to 100%. If the model fails to converge, then other correlation structures will be explored.

A sensitivity analysis using the PP Population will be provided for the proportion of subjects achieving a lesion count of 0 or 1 of all treatable MC at Week 12 and the proportion of subjects achieving at least a 90% reduction from Baseline in the number of all treatable MC at Week 12.

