### 11.3 Exploratory Analyses

Since the within-household correlation is expected to be small, the change and percent change from Baseline in the number of treatable MC at Weeks 2, 8 and 12 will be analyzed using a repeated measures mixed model for the respective visits with the same covariates as the primary model together with visits and treatment by visit; an unstructured covariance matrix will be utilized. If the calculation of the percent change from baseline is influenced by outliers with calculated values  $>100\%$ , then the influence of outliers will be avoided for analysis by censoring them so that all values were in the range of  $-100\%$  to  $100\%$ . If the model fails to converge, then other correlation structures will be explored.

The exploratory endpoints based on the proportion of subjects achieving complete clearance (at Weeks 2 and 4) or 75% (at Weeks 2, 4, 8, and 12) or 90% (at Weeks 2, 4, and 8) reductions will be analyzed in the same manner as the primary endpoint.

Likewise, the proportion of subjects achieving a lesion count of 0 or 1 of all treatable MC at Weeks 2, 4 and 8 will be analyzed in the same manner as the primary endpoint.

Since the within-household correlation is expected to be small and time to first complete clearance of all MC is exploratory, it will be analyzed using Kaplan-Meier methods. The number and percentage of subjects achieving complete clearance, number and percentage of censored subjects, and Kaplan-Meier estimates of first quartile, median, and third quartile will be summarized by treatment group. Differences in Kaplan-Meier curves between the treatments will be tested for significance using a stratified log-rank test.

The proportion of subjects who have a recurrence of MC after the first visit at which complete clearance was observed will be summarized.

The subject-reported spread of MC to household members not in the study will be summarized descriptively including a breakdown of whether or not there was any spread and then a breakdown of the amount of spread within the household at each visit at the household level.

A shift table comparing the baseline global severity assessment to each scheduled postbaseline assessment will be presented by subject and investigator. The Investigator and Subject Global Impression of change will be summarized descriptively.

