## 12. OTHER ANALYSES

The following analyses of BOTE vs lesion count will be presented:

- Percent change from Baseline in the number of treatable MC at each visit in relation to the Baseline BOTE score comparing No Inflammation vs Inflammation within each treatment group through a repeated measures mixed model with number of randomly assigned subjects in household (1 subject vs 2 subjects), investigator type (dermatologist

vs other), BOTE score at Baseline (no inflammation [BOTE=0] vs mild/moderate/severe/very severe inflammation [BOTE $\geq$ 1]), BOTE score at Baseline by visit interaction, age, and baseline lesion count as covariates with a compound symmetry covariance matrix.

- Percent change from Baseline in the number of treatable MC at Week 12 in relation to the highest post-baseline BOTE score during treatment will be summarized descriptively.
- Percent change from Baseline in the number of treatable MC at Week 12 in relation to the highest BOTE score at any visit (including Baseline) will be summarized descriptively.
- Percent change from Baseline in the number of treatable MC at each visit in relation to the BOTE score at Week 2 will be summarized descriptively.

In these analyses, the BOTE scores will be analyzed in the ITT Population as follows:

1. Dichotomized:
  - a. Score of 0: No Inflammation
  - b. Score of 1, 2, 3, or 4: Mild to Very Severe

A shift table comparing the baseline BOTE score to each scheduled post-baseline assessment will be presented for the ITT Population.

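### The exploratory model for absolute change in lesion count fixes one baseline-count slope across all visits, which probably makes the Week 12 interval somewhat too wide; letting the slope vary by visit is a free improvement

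*Protocol*

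**What the plan says.** Absolute change from Baseline in lesion count at Weeks 2, 4, 8 and 12 is an exploratory endpoint (Protocol 3, SAP 10.1). Protocol 10.3.6 analyses change and percent change with a repeated measures mixed model that has the "same covariates as the primary model together with visits and treatment by visit". SAP 11.3 keeps those terms and adds the covariance structure: "treatment by visit; an unstructured covariance matrix will be utilized".

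The covariates come from the primary model. Protocol 10.3.1 lists "age and Baseline lesion count as factors" among them. In SAP 11.1, baseline count is one linear term with one coefficient (X_Hi5 "is the subject's baseline lesion count"). Neither document crosses it with visit; in these models only treatment is crossed with visit.

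SAP 11.2 fits the same kind of model to percent change at Week 4, the fourth secondary endpoint, "with the same covariates as the primary model together with visits and treatment by visit interaction". The one other covariate-by-visit term in the SAP is in Section 12, in a separate model: "BOTE score at Baseline by visit interaction".

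**The concern.** Absolute change is the later count minus the baseline count. Early on, when counts have moved little, it depends only weakly on where the subject started. Once a subject clears, it equals exactly minus the baseline count. So the more clearance there is, the more negative the slope on baseline should become.

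The documents point to such a drift. Protocol 2.1.2.1 says counts often rise early in treatment. Protocol 2.1.4.3 shows clearance growing between Weeks 8 and 12: on SB206 from 15.3% to 25.8% in NI-MC301 and from 13.9% to 30.0% in NI-MC302; on vehicle from 10.3% to 21.6% and from 5.9% to 20.3%.

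A single slope is then a compromise that fits some visits badly, and variation that baseline count could explain stays in the residual. What is at stake is precision, not bias.

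**Working it through.** The plan states no standard error, SD or power for this model, so it has no figure to reproduce. The 90% power in Protocol 10.2.1 does reproduce (89.6% for 20% vs 29.5% with 425 per arm), but it concerns the primary endpoint and has no bearing here.

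**Inputs from the documents.** Mean baseline counts 18.1 and 18.3, and discontinuation 15.3% and 17.2%, in the earlier phase 3 studies (Protocol 2.1); baseline range 3 to 70 (Protocol 5.2); 425 per arm (Protocol 10.2.1).

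**Assumed, because the documents do not give them.** Baseline SD 12 to 16; residual SD 5 to 13; correlation between visits 0.5 exchangeable or 0.7 autoregressive; mean reduction of 5-10% at Week 2 rising to 45-60% at Week 12.

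**Step 1: the slope.** With X the baseline count and Y_t the count at visit t, the slope of Y_t - X on X is Cov(Y_t, X)/Var(X) - 1. If counts fall proportionally by a fraction f_t, the slope is -f_t. It is constant over visits only if f_t is.

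**Step 2: closed form.** Take complete data, residual covariance S and true visit slopes β_t. The fitted common slope is b = (1'S⁻¹β)/(1'S⁻¹1). The misfit (β_t - b)X goes into the residual, so

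SE ratio (common slope / visit-specific slopes) at visit t = √[1 + Var(X)(β_t - b)²/S_tt].

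Example: slopes -0.10, -0.20, -0.35, -0.45 at Weeks 2, 4, 8, 12; baseline SD 12 (variance 144); exchangeable correlation 0.5.

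| Residual SD by visit | b | Week 2 | Week 8 | Week 12 |
|---|---|---|---|---|
| 5, 8, 11, 13 | -0.080 | 1.001 | √(1 + 144×0.27²/121) = 1.043 | √(1 + 144×0.37²/169) = 1.057 |
| 10 throughout | -0.275 | √(1 + 144×0.175²/100) = 1.022 | √(1 + 144×0.075²/100) = 1.004 | 1.022 |
| 12, 11, 10, 9 | -0.358 | √(1 + 144×0.258²/144) = 1.033 | 1.000 | √(1 + 144×0.092²/81) = 1.008 |

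Which visit loses depends on how residual variance changes over time. Over the whole assumed grid the ratio runs from 1.01 to 1.23 at Week 12, 1.00 to 1.18 at Week 8 and 1.00 to 1.14 at Week 2. The top values at Weeks 8 and 12 need the steepest decline, baseline SD 16 and residual SD rising from 5 to 13. As a control, a slope held equal at all visits gives 1.00 throughout.

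**Step 3: simulation of absolute change, unstructured covariance.**

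- Model A: 425 per arm, baseline mean 18 and SD 13.5, proportional decline, about 16% dropout by Week 12. Model-based variance ratios at Week 12 were 1.08, 1.13 and 1.40 under weak, moderate and strong decline. Their square roots give SE ratios of 1.04, 1.06 and 1.18. Empirical variance ratios of 1.05, 1.09 and 1.33 give 1.02, 1.04 and 1.15. At Week 8, variance ratios of 1.08 (moderate) and 1.15 (strong) give SE ratios of 1.04 and 1.07.
- Model B: 850 subjects, gamma baseline counts cut to 3-70, Poisson-lognormal follow-up, 150 replicates, baseline count and treatment as the only covariates. Visit slopes were about -0.03, -0.14, -0.31 and -0.44, against a common slope of about -0.15. The Week 12 SE was 0.682 vs 0.632 (ratio 1.08) with complete data and 0.726 vs 0.665 (1.09) with 16% dropout. Week 8 ratios were 1.02 and 1.03; Week 2 was about 1.03. The two models' treatment estimates agreed within 0.02 lesions (at Week 12, -2.66 vs -2.67 and -2.59 vs -2.57).
- Model C: a further complete-data simulation with assumed inputs gave an SE 5-14% too wide at Week 12, 1-3% at Week 8 and up to 9% at Week 2 in one scenario.

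**Step 4: percent change.** In Model B the visit slopes were all about 0.01 to 0.03, and the SE ratio was 1.00 at every visit. Dividing by baseline removes the drift when decline is roughly proportional.

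**The case against.** The strongest reply is that nothing confirmatory depends on this. Absolute change is exploratory at every visit and lies outside the fixed testing sequence (Protocol 10.3.2, SAP 10.7). The estimate does not move, so neither bias nor false-positive risk arises. The size rests on variances and a decline pattern that the documents do not report. All of this stands, and it limits the point to an optional gain in precision.

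Several stronger readings are tempting, and the documents do not support them:

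- *That the Week 4 secondary endpoint is weakened.* It is a percent change, and the check finds no loss on that scale.
- *That Weeks 8 and 12 both lose materially.* The Week 8 loss was small in most simulations and vanishes if residual variance shrinks over time; Week 2 then loses most.
- *That the loss is 40%.* That is a variance ratio from the strongest decline only; on the standard-error scale it is about 18%.
- *That SAP 12 sets a precedent which 11.3 ignores.* In SAP 12, BOTE is the factor being compared within each arm, so its visit interaction does the job that treatment by visit does in 11.3. That model also keeps baseline count as a single term.
- *That the protocol is at fault.* Protocol 10.2.3 leaves the detail of exploratory analyses to the SAP.

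What the reply does not remove is that the term is absent, that a constant slope is implausible for absolute change under progressive clearance, and that adding the term is almost free.

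**Conclusion.** The point holds for one exploratory endpoint, absolute change, and mainly at Week 12. Across the simulations the Week 12 standard error of the treatment difference is roughly 2-18% too wide, with most scenarios at 4-9%. The closed form spans 1-23% at its extremes. A ratio of 1.08 to 1.09 is a variance ratio of about 1.16 to 1.19, or some 14-16% of the information on that contrast (1 - 1/1.16 to 1 - 1/1.19). Week 8 usually loses 1-3%, up to about 7% in simulation and more only at the edge of the closed-form grid. Week 2 may lose some precision.

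These sizes depend on the assumed baseline SD, residual variances, correlations and roughly proportional decline. The direction for absolute change needs only that clearance progresses over the visits. Primary and secondary conclusions are unaffected.

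**What to change.** In SAP 11.3, for absolute change from Baseline, add a baseline lesion count by visit interaction to the existing covariates, visit and treatment by visit, and keep the unstructured covariance. Record the addition in SAP 14.

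Do this before the Week 12 data are frozen and unblinded, because SAP 6 labels any later analysis post hoc. SAP 11.2 needs no change, and no BOTE by visit term is needed in the lesion-count models.

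The cost is one phrase and three parameters with about 850 subjects, with all four visits in the model. SAP 11.3 names only Weeks 2, 8 and 12 for change, whereas SAP 10.1 also lists absolute change at Week 4, so the edit should state which visits enter. No new data are needed and the primary analysis is untouched.
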